### 10.2. Secondary Efficacy Endpoints and Analyses

The binary variables for secondary endpoints include the following:

- The proportion of subjects achieving PASI-50, PASI-75, PASI-90, PASI-100 at all visits from Week 1 to Week 16
- The proportion of subjects achieving an sPGA score of "0" ("clear") or "1" ("almost clear") combined with 2-point reduction on the 5-point sPGA scale at all visits from Week 1 to Week 16
- The proportion of subjects with at least a 5-point reduction from baseline in the DLQI score at all visits from Week 1 to Week 16

The binary secondary endpoints will be analyzed using similar methods as described in [Section 10.1](#). Analysis of PASI-related secondary endpoints will be based on both FAS and PPS using complete case analysis, LOCF and NRI. In addition, analysis will be performed stratified by receipt of any biologics for psoriasis based on FAS. Analysis of the secondary endpoint of achieving an sPGA score of "0" ("clear") or "1" ("almost clear") combined with a 2-point reduction on the 5-point sPGA scale will be based on both FAS and PPS using complete analysis, LOCF and NRI. Analysis of the secondary endpoint of at least 5-point reduction from baseline in the DLQI score will be based on both FAS and PPS using complete case analysis only.

The continuous variables for secondary endpoints include the following:

This document is confidential.

- The percent change from baseline in PASI score at all visits from Week 1 to Week 16
- The change from baseline in affected BSA at all visits from Week 1 to Week 16
- The change from baseline in the itch NRS at all visits from Week 1 to Week 16
- The change from baseline in the DLQI score at all visits from Week 1 to Week 16

Descriptive statistics for the continuous secondary endpoints described above will be provided at each schedule visit by treatment group. Additionally, the secondary continuous efficacy endpoints (including percent changes for PASI, changes for DLQI, BSA and NRS) will be analyzed using a mixed-effect model for repeated measures (MMRM) with the change or percent change from baseline as the response variable, treatment group, visit, treatment-by-visit interaction as fixed effects, and the baseline value as a covariate. An unstructured covariance matrix will be used to model the correlation among repeated measurements. The Kenward-Roger adjustment will be used with restricted maximum likelihood (REML) to make proper statistical inference. The LS mean differences between ME3183 treatment groups and placebo at each scheduled visits along with the 2-sided 95% CIs and 2-sided p-values will be estimated from the MMRM model. In the event that MMRM with unstructured covariance matrix fails to converge, alternative covariance structures will be explored, including Toeplitz, heterogeneous Toeplitz, variance components, compound symmetry, heterogeneous compound symmetry, autoregressive and heterogeneous autoregressive covariance matrices, where the optimal covariance matrix structure will be selected based on Akaike's Information Criteria (AIC), where smaller values of AIC indicate better overall fit. MMRMs will be estimated for the secondary continuous efficacy endpoints using complete case analysis only.

Kaplan-Meier method will be used for summarizing the time to the first response of PASI-50 and PASI-75 in days. The time to the first response of PASI-50 and PASI-75 is defined as the number of days from the first dose of the study drug to the first response. If a subject does not achieve PASI-50 and PASI-75, the variable will be censored on the last PASI assessment date. Median time to response and 95% CI will be provided, when estimable. The CI will be based on log-log transformation. The reverse Kaplan-Meier plots of PASI-50 and PASI-75 will be presented by treatment group. The comparison of the time to PASI-50 and PASI-75 between each ME3183 treatment group and placebo will be performed using the log-rank test.

The Cox proportional hazard model will be used for analyzing the time to PASI-50 and PASI-75, where time to the first response of PASI-50 or PASI-75 will be used as outcome variables and treatment group will be included as covariates. Estimated hazard ratios along with 95% CIs and p-values between each ME3183 treatment group and placebo will be provided.

[figure not shown]
For the secondary endpoints of proportions of subjects achieving PASI-50, PASI-75, PASI-90, PASI-100 at all visits from Week 1 to Week 16 and percent change in PASI scores from baseline at all visits from Week 1 to Week 16, any missing PASI scores arising from intercurrent events will be imputed via LOCF and NRI, similar to the methods described in [Section 10.1](#) for the primary efficacy endpoints, in addition to the complete case analysis.

For PASI and DLQI, in addition to the total score, the region specific PASI scores (head, upper limbs, trunk, lower limbs) and the numerical responses for each of the ten questions in DLQI questionnaire will be summarized descriptively at each study visit for the actual values and changes from baseline for all post-baseline visits.

This document is confidential.

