#### 4.3. Determination of Sample Size

No formal sample size calculation was performed.

For the assessment of efficacy and safety of ME3183 in subjects with moderate to severe plaque psoriasis in this proof-of-concept study, approximately 125 eligible subjects will be enrolled. Twenty-five subjects will be randomized to each of the following treatment groups: ME3183 [REDACTED] mg BID, ME3183 [REDACTED] mg QD, ME3183 [REDACTED] mg BID; ME3183 [REDACTED] mg QD, and placebo. The number of planned subjects is considered adequate to assess safety and to provide efficacy estimates for in this Phase 2a study. The expected drop-out rate is assumed to be 10%.

This document is confidential.

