#### 4.4. Treatment Assignment and Blinding

##### 4.4.1. Method of Study Treatment Assignment

Prior to dosing on Day 1, all the eligible subjects will be randomly assigned to 1 of the 5 treatment groups in a 1:1:1:1:1 ratio. Subjects will be assigned a randomization number through interactive web response system (IWRS), in accordance with the randomization code generated by the authorized personnel at PPD [REDACTED] designated by PPD [REDACTED]. An unblinded, independent study statistician will be assigned to produce the randomization schedule. Once a randomization number is allocated to 1 subject, same number may not be assigned to another subject even if the former discontinued the study.

To promote balanced allocation, randomization will be stratified by the subject's receipt (yes/no) of previous treatment with a biologic drug for psoriasis. Bio-naïve subjects will be randomized above 50% of the planned total subject randomization.

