### 10.1. Primary Efficacy Endpoint and Analysis

The primary efficacy endpoint is the proportion of subjects achieving  $\geq 75\%$  reduction from baseline in the PASI score at Week 16. Baseline is defined as the PASI score on Day 1 pre-dose.

For each ME3183 treatment group, the difference in the proportion of subjects achieving the difference in PASI-75 (ME3183 – placebo) and its 95% confidence interval (CI) will be estimated and tested for superior treatment effect using the Cochran-Mantel-Haenszel (CMH) test with prior receipt of any biologics for psoriasis (bio-naïve vs non-bio-naïve) as adjustment factor at a 1-sided significance level of  $\alpha = 0.025$ .

Analysis will be conducted using observed data at Week 16 only (complete-case analysis). In the presence of missing data, additional sensitivity analysis will be conducted using both LOCF and NRI. Under LOCF, the last non-missing PASI score will be carried forward to Week 16, based on which the subject will be considered as responder or non-responder and summarized accordingly. Under NRI, subjects with missing PASI scores at Week 16 will be considered non-responders.

Subgroup analysis will be carried out stratified by the prior receipt of any biologics for psoriasis (bio-naïve vs non-bio-naïve), where Fisher's exact test will be used instead of CMH for superiority.

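### SAP 10.2 leaves the randomisation stratum, prior biologic use, out of the MMRM, log-rank and Cox analyses, although the primary test adjusts for it and adding it costs almost nothing

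*SAP*

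**What the plan says.** - **Design.** SAP 4.4.1 (as Protocol 7.1 and 9.3.1) states that "randomization will be stratified by the subject's receipt (yes/no) of previous treatment with a biologic drug for psoriasis". Bio-naïve subjects are to make up more than half of those randomised.
- **Primary analysis.** SAP 10.1 specifies the "CMH) test with prior receipt of any biologics for psoriasis" as adjustment factor.
- **Binary secondary endpoints.** SAP 10.2: "The binary secondary endpoints will be analyzed using similar methods as described in" Section 10.1, so they carry the same adjustment.
- **MMRM** (PASI percent change; change in BSA, itch NRS and DLQI). SAP 10.2 lists "treatment group, visit, treatment-by-visit interaction as fixed effects, and the baseline value as a covariate". Prior biologic use is not among them.
- **Time to PASI-50 and PASI-75.** The comparison "between each ME3183 treatment group and placebo will be performed using the log-rank test", with no strata mentioned. In the Cox model "treatment group will be included as covariates", and nothing else is named.

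Neither the secondary estimands (SAP 7.2) nor the MMRM and Cox table titles (SAP 18) add the factor. Protocol 15.3.2 names the three methods without covariates, and Protocol 15 leaves further detail to the SAP. No reason for the omission appears anywhere.

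**The concern.** The same PASI scores are analysed with the stratum when expressed as responder rates, and without it when expressed as percent change or time to response. The second group of analyses therefore matches neither the first nor the way subjects were randomised.

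Stratified randomisation balances the factor across arms. If the factor predicts outcome and is then left out of a linear model, its variation goes into the residual while the treatment contrast does not actually carry that variation. Standard errors come out too large and intervals are conservative. In a Cox model the effect takes a different form: the unadjusted hazard ratio is pulled towards 1, while its standard error is not inflated. The unstratified log-rank test loses some power. With 25 subjects per arm and no formal sample size calculation (SAP 4.3), recoverable precision is worth having.

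**Working it through.** **The plan's own figure.** 5 arms × 25 = 125, as stated. SAP 4.3 says no formal sample size calculation was done, so there is no planned power to reproduce.

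**Inputs from the documents.** Five arms of 25; 10% dropout, leaving about 112 (SAP 4.3); a two-level stratum with the experienced share below 50% (SAP 4.4.1); post-baseline visits at Weeks 1, 2, 4, 8, 12 and 16.

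**Assumed, because the documents are silent.** Experienced share p from 10% to 48%; stratum effect δ from 0 to 0.8 SD; baseline-outcome correlation 0.3; treatment effect 0.8 SD. For time to response: 30% response by Week 16 in bio-naïve placebo subjects, treatment hazard ratio (HR) 2.8, stratum HR 1, 0.5 or 0.3, and share 20% or 35%.

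**1. Cost of the extra MMRM term (single-visit view).** The model without the stratum has 6 parameters (intercept, 4 treatment, baseline). Residual df at N = 112 is 112 − 6 = 106, or 105 with the stratum. The 97.5% t quantile moves from 1.98260 to 1.98282, a rise of about 0.01%. In simulation with δ = 0, adjusting widened the interval by 0.05-0.11% and changed power by 0 to −0.5 points.

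**2. Cost of omission in the MMRM.** Omission raises the residual variance from 1 − 0.3² = 0.91 to 0.91 + δ²p(1 − p), so

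width ratio ≈ √(1 + δ²p(1 − p)/0.91).

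- δ = 0.5, p = 0.10: √(1 + 0.25 × 0.09/0.91) = √1.0247 = 1.012
- δ = 0.5, p = 0.48: √(1 + 0.25 × 0.2496/0.91) = √1.0686 = 1.034
- δ = 0.8, p = 0.10: √(1 + 0.64 × 0.09/0.91) = √1.0633 = 1.031
- δ = 0.8, p = 0.48: √(1 + 0.64 × 0.2496/0.91) = √1.1755 = 1.084

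A simulated Week 16 ANCOVA (blocks of 5 within stratum, 10% random dropout, 10,000 runs per scenario) agrees:

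| Stratum effect | Unadjusted CI wider by | Power points lost |
|---|---|---|
| 0 SD | no change | none |
| 0.2 SD | 0.1-0.5% | at most 0.4 |
| 0.5 SD | 1.1-3.5% | 0.9-2.1 |
| 0.8 SD | 3.0-8.8% | 1.4-5.5 |

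At 0.8 SD the nominal 95% interval covered 95.7-96.7%. Treatment estimates did not move.

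**3. Log-rank power** (25 v 25, responses seen only at scheduled visits, 3,000 runs):

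| Stratum HR | Share | Unstratified | Stratified | Difference (points) |
|---|---|---|---|---|
| 1 | 20% | 64.6% | 63.7% | −0.9 |
| 1 | 35% | 66.2% | 66.0% | −0.2 |
| 0.5 | 20% | 60.1% | 61.4% | +1.3 |
| 0.5 | 35% | 56.6% | 57.9% | +1.3 |
| 0.3 | 20% | 56.4% | 58.6% | +2.2 |
| 0.3 | 35% | 48.9% | 53.5% | +4.6 |

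A repeat simulation gave gains of 0.9-1.6 points at HR 0.5 and 2.5-3.9 at HR 0.3, with a cost of about 0.6 when the stratum is not prognostic. Under other assumptions (PASI-50: 30% placebo response, HR 3; PASI-75: 10%, HR 5), stratifying changed power by −1.4 to +4.7 points.

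**4. Cox model** (1,500 runs), median HR unadjusted v stratified:

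- Stratum HR 0.5: 2.76 v 2.80 (share 20%) and 2.75 v 2.82 (35%).
- Stratum HR 0.3: 2.72 v 2.80 (20%) and 2.69 v 2.84 (35%).

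The largest shift is ln(2.84/2.69) = 0.054 on the log scale. The unadjusted SE is marginally smaller (for example 0.521 v 0.523), so stratifying gives no SE gain.

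**The case against.** The strongest reply is that this is a modelling preference. These are secondary analyses in a Phase 2a trial, the SAP contradicts nothing in Protocol 15.3.2, no decision rule depends on them, and the consequence in the MMRM is conservative. All of that stands, and it is why the point is minor.

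Other parts of the reply:

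- **Subgroup summaries.** SAP 8.6 and 10.2 plan PASI summaries by prior biologic use, so a stratum difference in PASI would be visible. True, but those tables do not adjust the overall MMRM, log-rank or Cox comparisons.
- **Prognostic strength.** Exclusion criteria 17 and 18 (no failure on a biologic, fewer than two biologics) may narrow the difference between strata. This stands; the assumed range therefore starts at zero.
- **Single-visit proxy.** A Week 16 ANCOVA lets the stratum act freely at Week 16, whereas one main effect in an MMRM averages over visits. In a six-visit simulation (assumed AR(1) correlation 0.7, shares 20-48%) with an effect growing to 0.5 SD, the unadjusted Week 16 SE was 1.6-2.5% larger than with a main effect, against 2.0-3.2% with stratum-by-visit. At 0.8 SD it was 3.8-6.2% against 5.0-8.5%. The upper figures are thus somewhat high for a main-effect fix if the stratum effect builds up over treatment.
- **Log-rank close to neutral.** One rerun gained only 0.1-0.8 points at stratum HR 0.5 and lost 0.2-0.7 when not prognostic. The gain at HR 0.5 is indeed near simulation noise; the gain at HR 0.3 is not.
- **Sparse PASI-75 events.** Assuming 8% placebo response, HR 5 and stratum HR 0.5, the experienced stratum had no events in 12-49% of pairwise comparisons. The power cost stayed at or below 0.6 points, but the stratum then contributes nothing.
- **Cox shift.** It is small against an SE of about 0.52, and is a marginal versus conditional hazard ratio rather than bias. Agreed.

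**Conclusion.** The point holds and is minor. Prior biologic use is absent from all three analyses without explanation, while the design, the primary test and the binary secondary endpoints use it. Validity is not at risk.

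The loss depends entirely on how prognostic the stratum is, which the documents do not say. It is nil if the stratum is not prognostic, a few per cent of MMRM interval width at 0.5 SD, and up to about 9% at 0.8 SD with a nearly even split. For time to response, the loss is about one log-rank power point at stratum HR 0.5 and roughly two to five at 0.3, with a small attenuation of the Cox hazard ratio. The case rests on consistency with the design plus a low cost, not on a demonstrated large gain.

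**What to change.** In SAP 10.2:

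- Add prior biologic use (yes/no), the factor already used in 10.1, as a fixed effect in each MMRM. If its effect is expected to develop over time, stratum-by-visit is an option at five further parameters (six visits).
- Specify a stratified log-rank test, and a Cox model stratified by the factor rather than with it as a covariate. A covariate coefficient cannot be estimated if one stratum has no PASI-75 responders.
- State whether the IWRS stratum or the eCRF value is used, here and in 10.1, since mis-stratification is a listed deviation type in SAP 6.8.
- Otherwise, give the reason for leaving the factor out.

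**Cost.** SAP wording and programming only; the variable is already collected. Each MMRM spends one parameter on the main effect. The Cox hazard ratio becomes conditional on stratum. If the factor is not prognostic, stratifying the log-rank test cost 0.2-0.9 power points in the main simulation and at most 1.4 in the other scenarios run, the latter within or near simulation error.

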	
Follow-up Period assessments will be performed on Day 141.
 
After the Screening Period, approximately 125 eligible subjects with a confirmed diagnosis of psoriatic plaques, a BSA involvement of $\geq 10\%$ (at Screening and Baseline), a PASI score 12 to 40 (at Screening and Baseline), and an sPGA ≥ 3 (at Screening and Baseline) will be randomly assigned to receive ME3183 [] mg twice daily [BID], [] mg once daily [QD], [] mg BID, or [] mg QD) or placebo in a 1:1:1:1 ratio. To promote balanced allocation, randomization will be stratified by the subject's receipt (yes/no) of previous treatment with a biologic drug for psoriasis. Bio-naïve subjects will be randomized above 50% of the planned total subject randomization.
 
After randomization (Day 1), all subjects will be evaluated at Baseline and at Weeks 1, 2, 4, 8, 12, 16, and 20. Efficacy assessments (ie, PASI, BSA, sPGA, and PRO assessments [DLQI and the itch NRS]), will be assessed at Baseline (Day 1) and at Weeks 1, 2, 4, 8, 12, 16, and 20. Blood samples for PK assessment will be collected predose at Weeks 1, 4, 8 and 16. Blood samples for [] assessments will be collected predose at Baseline (Day 1), Weeks 4 and 16. Safety and tolerability will be assessed by physical exam, monitoring for AEs and serious AE (SAEs), demographics, medical history, vital signs and safety laboratory tests (hematology, coagulation, blood chemistry, and urinalysis) at Baseline (Day 1) and Weeks 1, 2, 4, 8, 12, 16, and 20. ECGs will be assessed at Baseline (Day 1) and Weeks 4, 8, 12, 16, and 20.

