### 5.2. Secondary Efficacy Endpoints

- The percent change from baseline in PASI score at all visits from Week 1 to Week 16
- The proportion of subjects achieving PASI-50, PASI-75, PASI-90, PASI-100 at all visits from Week 1 to Week 16
- Time to PASI-50 and PASI-75
- The proportion of subjects achieving a Static Physicians Global Assessment (sPGA) score of “0” (“clear”) or “1” (“almost clear”) combined with 2-point reduction on the 5-point sPGA scale at all visits from Week 1 to Week 16
- The change from baseline in affected body surface area (BSA) at all visits from Week 1 to Week 16
- The change from baseline in the itch numerical rating scale (NRS) at all visits from Week 1 to Week 16
- The change from baseline in the Dermatology Life Quality Index (DLQI) score at all visits from Week 1 to Week 16
- Percentage of subjects with at least a 5-point reduction from baseline in the DLQI score at all visits from Week 1 to Week 16

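### The MMRMs for BSA, DLQI and itch fit one baseline slope to all six visits; a baseline-by-visit term is a cheap change that may recover precision at Week 16

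*SAP*

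**What the plan says.** SAP 10.2 fits each continuous secondary endpoint by MMRM "with the change or percent change from baseline as the response variable". PASI enters as percent change; BSA, itch NRS and DLQI enter as absolute change. The mean model is "treatment group, visit, treatment-by-visit interaction as fixed effects, and the baseline value as a covariate". The only interaction named is treatment by visit.

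On covariance, the SAP states: "An unstructured covariance matrix will be used to model the correlation among repeated measurements". If that fails to converge, simpler structures are compared by AIC. Estimation is by REML with Kenward-Roger. Differences from placebo at each visit, "along with the 2-sided 95% CIs and 2-sided p-values will be estimated from the MMRM model", are reported.

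The protocol synopsis says the efficacy measures "will be assessed at Baseline (Day 1) and at Weeks 1, 2, 4, 8, 12, 16, and 20". SAP 5.2 limits the endpoint window, for example "The change from baseline in affected body surface area (BSA) at all visits from Week 1 to Week 16", which leaves six post-baseline visits: Weeks 1, 2, 4, 8, 12 and 16. Protocol 15.3.2 commits to an MMRM only where applicable and does not give its terms. Neither document mentions a baseline-by-visit term.

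**The concern.** A subject who starts with a larger affected area has more to lose. If improvement is roughly proportional to baseline, the slope of absolute change on baseline is shallow early and steeper late. A model with one slope must compromise across visits. Under an unstructured covariance the compromise favours visits with small residual variance, which for change scores tend to be the early ones. The Week 16 difference would then be corrected for chance baseline imbalance by too small an amount, and baseline variation that could have been removed stays in the error. With 25 subjects per arm, and results meant to guide the next study's regimens, precision at Week 16 is worth keeping if it costs little.

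**Working it through.** **Inputs from the documents.** Five arms of 25 (N = 125); 10% dropout (125 × 0.9 = 112.5, about 112 at Week 16); six visits; two-sided 95% intervals. Neither document gives an SD, effect size, power or baseline correlation for BSA, DLQI or itch, so there is no figure of the plan's own to reproduce.

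**Formula (large sample, complete data).** Let β_t be the baseline slope at visit t, S the residual covariance given baseline, and σ² the baseline variance. The common slope converges to

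b = (1′S⁻¹β) / (1′S⁻¹1).

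The Week 16 estimate is the raw difference in mean change minus b times the difference in baseline means. Relative to a model with visit-specific slopes, its variance is multiplied by

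V = 1 + (β₁₆ − b)² σ² / S₁₆,₁₆.

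With r_t the correlation of baseline with the score at visit t, β_t = r_t(SD_t/SD_0) − 1 and S₁₆,₁₆ = SD₁₆²(1 − r₁₆²). If power is 80% with visit-specific slopes, it is Φ(2.802/√V − 1.960) with the common slope.

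**Assumed range, not from the documents.** r₁ from 0.7 to 0.9; r₁₆ from 0.3 to 0.7; SD₁₆ from 0.7 to 1.3 times SD₀; three within-subject correlation structures; 78 scenarios in all.

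**Worked case.** r falling from 0.9 to 0.5 with equal SDs: β₁ = −0.10, β₁₆ = −0.50, S₁₆,₁₆ = 0.75. One structure gives b = −0.12, so V = 1 + 0.38²/0.75 = 1.19 (1.197 with b unrounded).

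| r₁, r₁₆, SD ratio | β₁ | β₁₆ | b | V | Power | Equivalent n per arm (25/V) |
|---|---|---|---|---|---|---|
| 0.7, 0.7, 1.0 | −0.30 | −0.30 | −0.30 | 1.00 | 80% | 25.0 |
| 0.8, 0.5, 1.0 | −0.20 | −0.50 | −0.28 | 1.067 | 77.4% | 23.4 |
| 0.9, 0.5, 1.0 | −0.10 | −0.50 | −0.12 | 1.197 | 72.6% | 20.9 |
| 0.9, 0.3, 0.7 | −0.10 | −0.79 | −0.19 | 1.817 | 54.7% | 13.8 |

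The table uses one correlation structure. The other two give V = 1.166 and 1.213 in the third row. Over all 78 scenarios V runs from 1.00 to 1.82, with quartiles 1.02, 1.06 and 1.19. The matching power is 79.3%, 77.6% and 72.8% at the quartiles and 54.7% at the extreme.

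**Simulation check.** 5 × 25 subjects, six visits, complete data, 3,000 runs in each of six scenarios.
- For r from 0.9 to 0.5 with equal SDs, the Week 16 variance ratio was 1.16 to 1.22 and power 71–73% against 79–80%.
- For r from 0.8 to 0.5 with SD ratio 0.7, the ratio was 1.14 (74% against 80%).
- For equal slopes it was 0.99 (79% with either model).
- Type I error of the common-slope model was 4.5–5.3%. Its largest mean error was 0.010 baseline SD. The Monte Carlo standard error in that scenario is 0.263/√3000 = 0.005, so this is compatible with no bias.

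**Endpoint-like simulation.** 1,500 trials per scenario, with assumed proportional improvement rising from 10% to 50% on drug. The Week 16 standard error was 11% (BSA), 7% (DLQI) and 3% (itch) larger, so variance was 1.11² = 1.23, 1.07² = 1.14 and 1.03² = 1.06 times as large. Power was 77% against 83%, 70% against 76% and 77% against 81%. A less favourable DLQI setting gave only 82% against 83%.

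**Cost of the extra term.** Six slopes replace one, so five parameters are added. If the slopes are equal, the variance penalty is at most about 1/(N − 7): 1/118 = 0.85% at N = 125 and 1/105 = 0.95% at N = 112.

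**The case against.** A single baseline covariate in an MMRM is a legitimate prespecified analysis, and the loss depends on slopes that the documents do not give. A quarter of the assumed scenarios lose under 2% of variance, and median power falls only from 80% to 77.6%. Regression to the mean also narrows the gap. In the endpoint-like simulation, with 10% early improvement, the first-visit slopes were already −0.18 for DLQI and −0.26 for itch, steeper than −0.10; this is why itch loses little. The endpoints are secondary, no sample size was formally calculated, the primary PASI-75 analysis is untouched, and no success rule rests on these p-values. All of this stands. It limits the weight of the point but gives no reason to prefer the common slope.

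Three stronger readings are tempting, and the documents do not support them:
- **That the Week 16 comparisons are biased.** For a given baseline imbalance the estimate does shift by (β₁₆ − b) times that imbalance. This is the same term that inflates the variance, so it is not a second harm. It averages to zero over randomization, and the unstructured covariance absorbs the misfit, so the standard error is larger but honest.
- **That precision is certainly lost and the remedy is free.** The loss is zero if slopes are equal, and the added term has a small cost.
- **That percent change in PASI suffers equally.** Under proportional improvement, percent change has little baseline slope at any visit, and no gain has been shown there.

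**Conclusion.** The point holds as one of efficiency. As written, the model applies one baseline slope to six visits. If the slope of absolute change on baseline steepens over time, the Week 16 contrasts for BSA, DLQI and itch are under-adjusted. The plausible size is a Week 16 variance 0 to about 20% larger, equivalent at the upper end to about 21 instead of 25 subjects per arm. It is more in extreme scenarios and nil with equal slopes. These figures rest on assumed correlations and SDs, complete data and an unstructured covariance. The 10% dropout, the exact Kenward-Roger correction and the AIC-selected fallback structures were not simulated; with dropout, a misspecified mean model could add a small bias. The case for acting is the asymmetry: at most about 1% of variance is risked for a gain that may be many times that. It is a cheap improvement to secondary analyses.

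**What to change.** Before unblinding, add a baseline-by-visit interaction as a fixed effect to the MMRMs for BSA, DLQI and itch NRS in SAP 10.2. Keep every other term, the covariance strategy and the Kenward-Roger inference. The same term may go into the PASI percent-change model for consistency, though little gain is expected there. The cost is one line in the SAP, one model term in the program and the small penalty shown above; no new data are needed. After unblinding the change would be post hoc and should be labelled so.
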